#### **11.5 Physical Examination**

Abnormal physical exam (PE) findings will be summarized by body system and visit using counts and percentages.

#### **11.6 Karnofsky Performance Status (KPS)**

Karnofsky Performance Status Scale results, both raw and change and percentage change from baseline, will be summarized by visit using descriptive statistics.

#### **11.7 Concomitant Medications**

Concomitant medications (non-ITP) and ITP concomitant medications will be summarized at the patient level by World Health Organization (WHO) Anatomical Therapeutic Chemical (ATC) class 3 and preferred term using counts and percentages.

### **12.0 OTHER ANALYSES**

#### **12.1 Pharmacokinetics**

A separate document will describe the analyses of pharmacokinetic data.

## 12.2 SF-36

Descriptive statistics will be presented by scheduled visit for the actual values and the changes from baseline for the following:

- Eight domains: physical functioning, role physical, bodily pain, general health, vitality, social functioning, role emotional, and mental health, respectively
- Two summary scores: physical health summary and mental health summary, respectively
- Proportions of patients with change from baseline  $\geq 8$  at month 12 for each domain and summary score, respectively, will be presented

## 12.4 Protocol Deviations

Protocol deviations will be maintained in the trial master file and will be listed and discussed in the clinical study report.

## 12.5 Rescue Therapy

A rescue therapy event is defined based on the medication administration start date. Two or more rescue medications started on the same day are counted as one rescue therapy event. Only rescue medications administered on or after the first dose of study drug in the present study are included.

The number of rescue therapy events per patient will be summarized using descriptive statistics for the following:

- Placebo patients of the C-935788-047/C-935788-048 study who received rescue therapy prior to Week 10 (Day 73)
- Placebo patients of the C-935788-047/C-935788-048 study who received rescue therapy after Week 10

The number and percentage of patient who received any rescue therapy in the present study will be summarized for

- the placebo patients of the C-935788-047/C-935788-048 study who received rescue therapy prior to Week 10 (Day 73)
- the placebo patients of the C-935788-047/C-935788-048 study who received rescue therapy after Week 10,
- all patients in C-935788-049 study

In addition, the number of patients who received any rescue therapy will be summarized using counts and percentages, and the number of rescue therapy events per patient for all patients who

received any rescue therapy will be summarized using descriptive statistics. These analyses above will be conducted by prior study treatment group and overall.

**14.0 APPENDICES**

## 14.1 Additional Exploratory Efficacy Endpoints and Other Endpoints

- [Redacted]
- [Redacted]
- [Redacted]
- [Redacted]
- [Redacted]
- [Redacted]
- [Redacted]

## 14.2 Additional Definitions of Duration of Platelet Response and Total Duration of Platelet Response

The additional definitions of duration of platelet responses are presented as follows:

- 1) The length of time from when the patient first achieves a platelet count of at least 50,000/ $\mu$ L until the loss of platelet response, which is defined as the earlier time of (the first of two consecutive visits with platelet counts < 30,000/ $\mu$ L that are at least 4 weeks apart or the first use of rescue therapy after first achieving a platelet count of at least 50,000/ $\mu$ L)
- 2) The length of time from when the patient first achieves a platelet count of at least 50,000/ $\mu$ L until the loss of platelet response, which is defined as the earlier time of (the first of two consecutive visits with platelet counts < 20,000/ $\mu$ L that are at least 4 weeks apart or the first use of rescue therapy after first achieving a platelet count of at least 50,000/ $\mu$ L)
- 3) The length of time from when the patient first achieves a platelet count of at least 30,000/ $\mu$ L until the loss of platelet response, which is defined as the earlier time of (the first of two consecutive visits with platelet counts < 30,000/ $\mu$ L that are at least 4 weeks apart or the first use of rescue therapy after first achieving a platelet count of at least 30,000/ $\mu$ L)
- 4) The length of time from when the patient first achieves a platelet count of at least 30,000/ $\mu$ L until the loss of platelet response, which is defined as the earlier time of (the first of two consecutive visits with platelet counts < 20,000/ $\mu$ L that are at least 4 weeks apart or the first use of rescue therapy after first achieving a platelet count of at least 30,000/ $\mu$ L)

Patients who drop out of the study before achieving a platelet response [i.e., achieving a platelet count of  $\geq$  50,000/ $\mu$ L for definition 1)-2) or  $\geq$  30,000/ $\mu$ L for definitions 3) - 4)] will be assigned a value of 0 for this endpoint. Patients who drop out of the study by the time of database lock while still maintaining a platelet response will be censored as of the time of the last platelet measurement prior to drop out of study respectively. Similarly, patients who remain in the study by the time of database lock while still maintaining a platelet response will be censored as of the time of the last platelet measurement prior to the time of database lock. For patients who have achieved and are maintaining a platelet response but who have discontinued treatment due to lack of efficacy or to an AE by the time of database lock, duration of platelet response will be defined as the time from first achieving a platelet response [i.e., achieving a platelet count of  $\geq$  50,000/ $\mu$ L for definition 1)-2) or  $\geq$  30,000/ $\mu$ L for definitions 3)- 4)] until discontinuation of treatment.

For each of additional definitions of duration of platelet responses 1)-4) above, the total duration of platelet response will be defined as the sum of all durations of platelet responses.

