7.1 Treatment Period

7.1.1 Enrollment (Day 1)

Subjects must be willing to sign and date an Institutional Review Board (IRB)/Independent Ethics Committee (IEC) approved informed consent form (ICF) prior to participating in any study-specific procedure activities. Subjects will retain their same Subject ID number as per Study C-935788-047 or C-935788-048, as applicable.

Subjects who have completed the Week 24 assessments in the previous ITP study within 7 days of enrollment in the extension study do not need to repeat these same assessments. The assessments performed during the Week 24 visit in the prior ITP study will be used to qualify subject for enrollment in the extension study. The subject must sign the ICF prior to enrollment in the extension study. The following assessments must be performed in order for a subject to be eligible for the extension study.

All local and central laboratory results must be reviewed for eligibility prior to enrollment.

- Inclusion/Exclusion Criteria
- SF-36, (must be administered prior to any other study specific procedures (refer to [Appendix 5](#))
- Physical examination, vital signs, and KPS (refer to [Error! Reference source not found.](#))
- Concomitant medications
- Bleeding Assessments by ITP Bleeding Scale (IBLS) (refer to [Appendix 7](#))
- 12-lead electrocardiogram (ECG)
- Complete blood count (CBC) with differential and reticulocyte count
- Platelet count (performed at institutional or local lab)
- Serum chemistry
- Immunoglobulin levels
- Urinalysis
- Pregnancy test (for females of childbearing potential)
- AEs

Table 2: Schedule of Study Procedures

	Day 1 Screen/ Enrollment^a	End of Month 1 (± 3 days)	Months 2–18 (± 3 days)	Months 19–60 (± 1 week)	Follow-up (± 7 days)ⁱ
Informed consent	X				
Inclusion/Exclusion	X				
Physical exam/KPS	X	X	monthly	every other month	X
Concomitant medications	X	X	monthly	every other month	X
Vital signs ^b	X	X	monthly	every other month	X
Bleeding assessment ^c	X	X	monthly	every other month	X
ECG	X				
Hematology ^d	X		monthly	every other month	X
Platelets	X	X	monthly	every other month	X
Serum chemistries (including LFTs) ^e	X		Months 4, 8, 12, 16	every other month	X
LFTs only ^f			monthly (in months full serum chemistries not done)		X
Immunoglobulin levels	X				X
Urinalysis	X		Months 4, 8, 12, 16	every 4 months	X
Urine pregnancy test ^g	X		every other month	every other month	
SF-36 ^h	X		Month 12		
AEs	X	X	monthly	every other month	X
PK			Month 2		

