7.1.2 Treatment Visits

The treatment period begins at the time of enrollment and may continue up to a total of 60 months. Over the course of the study, subjects will be expected to visit the clinic monthly for the first 18 months, followed by every 2 months for the remainder of the study. Assessments including platelet counts will be performed to evaluate the safety and efficacy of fostamatinib, and to determine if a dose adjustment is required. All visits are determined by the date of enrollment and should occur within the windows specified (refer to Table 2 for the complete schedule of study procedures).

[figure not shown]
Study drug accountability will be performed at each visit. New bottle of fostamatinib will be dispensed using the IWRS at each visit. Used bottles will be returned for accountability. At the final visit of the treatment period, final study drug accountability will be performed.

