## 3.0 INVESTIGATIONAL PLAN

### 3.1 Overall Study Design Summary

This is a Phase 3 multi-center, open label extension study to evaluate the long-term safety and efficacy of fostamatinib in achieving and maintaining a stable platelet response in subjects with persistent/chronic Immune Thrombocytopenic Purpura (ITP). For the purpose of this study, the term ‘subject’ will refer to patients with persistent/chronic ITP participating in this study. Up to 150 subjects will be enrolled at multiple sites. The study will consist of monthly visits for 18 months followed by every-other-month visits for a maximum of 5 years of treatment or until commercial availability of drug, whichever comes first.

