**Table 1: Schedule of Study Procedures**

	Day 1 Screen/ Enrollmenta	End of Month 1 (± 3 days)	Months 2–18 (± 3 days)	Months 19– 60 (± 1 week)	Follow-up (± 7 days)i
Informed consent	X				
Inclusion/Exclusion	X				
Physical exam/KPS	X	X	monthly	every other month	X
Concomitant medications	X	X	monthly	every other month	X
Vital signs b	X	X	monthly	every other month	X
Bleeding assessment c	X	X	monthly	every other month	X
ECG	X				
Hematology d	X		monthly	every other month	X
Platelets	X	X	monthly	every other month	X
Serum chemistries (including LFTs) e	X		Months 4, 8, 12, 16	every other month	X
LFTs only f			monthly (in months full serum chemistries not done)		X
Immunoglobulin levels	X				X
Urinalysis	X		Months 4, 8, 12, 16	every 4 months	X
Urine pregnancy test g	X		every other month	every other month	
SF-36 h	X		Month 12		
AEs	X	X	monthly	every other month	X
PK			Month 2		
Study drug dispensed/Accountability	X	X	monthly	every other month	
Dose adjustment (prn)	X	X	monthly	every other month	

- a. **Screen/Enrollment (Day 1):** These procedures are equivalent to Week 24 visit of Study C-935788-047 or C-935788-048; assessments performed as part of Week 24 may be used to assess subject's eligibility to roll over and do not need to be repeated specific to Study C-935788-049.
- b. **Vital Signs:** blood pressure, pulse and temperature
- c. **Bleeding assessment:** IBLS scale only; prior to Version 4, protocol used both IBLS and WHO bleeding scales
- d. **Hematology:** CBC with differential, RBC, hemoglobin, hematocrit, MCHC, MCH, MCV, MPV, RDW, reticulocytes
- e. **Serum chemistries:** Na, K, Cl, bicarbonate (CO2), Ca, PO4, BUN, creatinine, globulin, glucose, LDH, AST, ALT, alkaline phosphatase, total bilirubin, total protein, albumin
- f. **LFTs:** ALT, AST, ALP, LDH, and bilirubin (total and direct)
- g. **Pregnancy Test:** For women of childbearing potential, regardless of birth control methodology
- h. **SF-36:** At visits where the SF-36 is evaluated the SF-36 must be the first assessment performed.
- i. **Follow-up visit:** to be completed approximately 2 weeks (+/- 7 days) after subject's last treatment or at the time of early treatment termination.

[figure not shown]

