#### 4.4. Secondary Efficacy Endpoints

The secondary efficacy endpoints are as follows:

- The duration of platelet response (months) and total duration of platelet response (months)
- Patients with reduction in the dose of concomitant ITP therapy while maintaining an adequate platelet count (yes/no)

Duration of platelet response will be defined as the length of time from when the patient first achieves a platelet count of at least 50,000/ $\mu$ L until the first of two visits with platelet counts < 50,000/ $\mu$ L that are at least 4 weeks apart without an intervening visit with a platelet count  $\geq$  50,000/ $\mu$ L unrelated to rescue therapy.

Four additional definitions of duration of platelet responses are stated in **Appendix 14.2**

Patients who drop out of the study before achieving a platelet response (i.e., achieving a platelet count of  $\geq$  50,000/ $\mu$ L) will be assigned a value of 0 for this endpoint. Patients who drop out of the study by the time of database lock while still maintaining a platelet response will be censored as of the time of the last platelet measurement prior to dropping out of the study. Similarly, patients who remain in the study by the time of database lock while still maintaining a platelet response will be censored as of the time of the last platelet measurement prior to the time of database lock. For patients who have achieved and are maintaining a platelet response but who have discontinued treatment due to lack of efficacy or to an AE by the time of database lock, duration of platelet response will be defined as the time from first achieving a platelet count of  $\geq$  50,000/ $\mu$ L until discontinuation of treatment.

The total duration of platelet response is defined as the sum of all durations of platelet responses.

Regarding the secondary efficacy endpoint of patients with reduction in the dose of concomitant ITP therapy while maintaining an adequate platelet (yes/no), a patient is said to have reduction while maintaining an adequate platelet count if the date of reduction of dose of concomitant ITP therapy occurs within the span of the duration of a platelet response during the C-935788-049 study and the reduction was not prompted by AE.

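### The four additional loss-of-response definitions in SAP 14.2 require low counts at adjacent visits that are also 4 weeks apart, so loss can be dated late or missed

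*SAP*

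**What the plan says.** SAP 14.2 gives four additional definitions of duration of platelet response. Response starts at 50,000/µL (definitions 1 and 2) or 30,000/µL (3 and 4). Loss is the earlier of two events. The platelet limb is "the first of two consecutive visits with platelet counts" below 30,000/µL (definitions 1 and 3) or 20,000/µL (2 and 4), "that are at least 4 weeks apart or the first use of rescue therapy after first achieving" the response threshold; those last words also give the rescue limb. Discontinuation for lack of efficacy or an AE ends the duration on the discontinuation date.

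The main definition in SAP 4.4 reads differently. It needs two low visits "that are at least 4 weeks apart without an intervening visit with a platelet count" at or above 50,000/µL unrelated to rescue. The two visits need not be adjacent.

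On timing, SAP 3.1 states: "The study will consist of monthly visits for 18 months followed by every-other-month visits". The schedule table allows ±3 days through Month 18 and ±1 week from Month 19. Protocol 7.1.2 anchors the windows: "All visits are determined by the date of enrollment and should occur within the windows specified".

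SAP 10.2.1 and 10.2.2 apply the main definition's analyses, Kaplan-Meier included, to the additional definitions and their totals.

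**The concern.** Adjacency and a 28-day minimum work against each other. A rule for sustained loss should be easier to satisfy as low counts accumulate. Under 14.2, an additional low count can instead split a qualifying pair into two short gaps, neither of which qualifies. Even without extra counts, the ±3-day window lets two correctly scheduled monthly visits fall under 28 days apart.

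Both effects act in one direction: loss is dated too late or not recorded, and low-count time is credited as response. The additional durations and their totals are therefore lengthened, most for patients counted most often.

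**Working it through.** The plan states no figure for this, so there is nothing to reproduce.

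**Inputs**
- Minimum spacing: 28 days (SAP 14.2).
- Window: ±3 days around each monthly target through Month 18, anchored to enrollment (schedule table; Protocol 7.1.2).
- Month length M: 30 days (Protocol 7.2.1 places the end of Month 1 at about Day 30) or 28 days (Protocol 7.3 equates 3 months with 12 weeks). M = 31 is added as a calendar-month sensitivity.
- Assumption: visit days independent and uniform over the seven days of the window.

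**Scheduled visits through Month 18.** The gap between adjacent visits is M + e2 − e1, with each e in {−3, …, +3}, giving 49 pairs. The number of pairs with e2 − e1 = −d is 7 − d.

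| M (days) | Gap range (days) | Gap under 28 requires | Pairs | Share |
|---|---|---|---|---|
| 30 | 24–36 | d ≥ 3 | 4+3+2+1 = 10 | 20.4% |
| 31 | 25–37 | d ≥ 4 | 3+2+1 = 6 | 12.2% |
| 28 | 22–34 | d ≥ 1 | 6+5+4+3+2+1 = 21 | 42.9% |

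With two patterns that concentrate visits on the target day, the shares are about 11–14% (M = 30), 4–6% (M = 31) and 39–41% (M = 28). Visits exactly on target never miss.

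**Consequence for a patient who stays low.** Take M = 30 and low counts on days 182, 208 and 240. The adjacent gaps are 26 and 32 days. Under 14.2 the first pair fails and loss is dated to day 208. Under the 4.4 pattern, days 182 and 240 are 58 days apart with no recovery, so loss is dated to day 182. In a simulation of 100,000 patients, loss was dated late in about 21% (mean 26 days late when delayed) for M = 30 and 43% (mean 32 days) for M = 28.

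**Three low visits in a row.** Under 14.2 the loss is missed if both gaps are short: 1/343 = 0.3% (M = 30) or 35/343 = 10.2% (M = 28). Under the 4.4 pattern it is never missed, because three visits span at least 2 × 30 − 6 = 54 or 2 × 28 − 6 = 50 days. A dip confined to two visits under 28 days apart is missed under both rules.

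**Extra counts.** If a count is added on day x of a 30-day interval, the longer piece is max(x, 30 − x). This is under 28 for x = 3 to 27, so that interval no longer holds a qualifying pair. Low counts on days 180, 195 and 210 give gaps of 15 and 15: no loss under 14.2, but loss on day 180 under the 4.4 pattern. With counts every 3.5, 7, 14 or 21 days, no adjacent pair qualifies while that spacing lasts.

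**From Month 19.** The smallest in-window gap between every-other-month visits is 60 − 14 = 46 days, or 56 − 14 = 42 for 28-day months. The rule can always be met.

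**The case against.** A reader might infer that a patient with weekly counts below 20,000/µL for months never loses response under definitions 1 to 4. The documents do not support that. First rescue ends response, as does discontinuation for lack of efficacy or an AE, and Protocol 7.3 provides for discontinuing patients whose counts stay below 50,000/µL after 12 weeks, with exceptions. Nothing schedules weekly platelet counts, and nothing says that extra counts are likeliest when platelets are lowest. What stands is narrower: while all counts are under 28 days apart, the platelet limb alone cannot be met, and a later discontinuation dates the end after the first low count.

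Even that depends on what counts as a visit. SAP 11.3 includes unscheduled visits for maximum and last blood pressure; SAP 10.3 summarises platelets by scheduled visit; SAP 14.2 is silent. If only scheduled visits count, the extra-count problem disappears within this study. SAP 5.1 also brings prior-study data into duration of response, but the documents do not give that visit interval. The silence is itself a gap to close.

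It is also tempting to shorten the minimum to 24 days in SAP 4.3 and 4.4. Those endpoints come from Protocol 10.4.1 and 10.4.2, lack the adjacency condition, and would be changed after the interim analysis noted in SAP 5.4. A 4-week persistence rule may intend to ignore shorter dips. Twenty-four days would also not cover every window: with 28-day months, 3/49 pairs (6.1%) are still closer. In the 12-week Version 2 period, whether a third monthly visit can confirm loss depends on month length: it falls inside for 1/49 offset pairs at 30 days and 28/49 at 28 days. This does not justify redefining the endpoint.

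**Conclusion.** The point holds as a minor defect in SAP 14.2. The adjacency condition departs from SAP 4.4 without a stated reason and can only delay or suppress a recorded platelet loss. On scheduled visits through Month 18, about 20% of adjacent pairs miss the 28-day minimum under 30-day months and uniform visit days, with a range of about 4% to 43% across the month lengths and visit patterns tried. For a patient who stays low, the usual effect is a loss dated about one visit late; complete misses mainly affect two-visit dips. The extra-count effect is conditional on unscheduled or closely spaced prior-study counts being treated as visits.

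The additional definitions are descriptive variants of a secondary endpoint in a study whose primary objective is safety. The main duration in SAP 4.4 and both versions of the primary efficacy endpoint do not require adjacency.

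**What to change.** Reword the platelet limb of definitions 1 to 4 on the SAP 4.4 pattern: loss occurs at the first of two visits below the definition's loss threshold, at least 4 weeks apart, with no visit at or above that threshold in between. Keep first rescue as the alternative trigger. State that unscheduled platelet counts qualify as visits.

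Leave the 4-week minimum in SAP 4.3 and 4.4 as it is. A shorter minimum matched to the visit window could be run, but only as a labelled sensitivity analysis.

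The cost is one wording change, repeated in four definitions found only in the SAP, and slightly shorter durations and totals under them. The rewording does not capture an isolated two-visit dip under 28 days apart; that remains a consequence of the 4-week rule.

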3.3 Clinical Development of Fostamatinib in ITP

A Phase 2 pilot trial (Study C-935788-007) in adults with persistent/chronic ITP (defined as platelet count $< 30,000/\mu\text{L}$ for ≥ 3 months) is ongoing (now as an investigator sponsored study).⁽¹⁾ All patients had failed at least 2 standard therapeutic regimens. Patients were treated with escalating doses of fostamatinib in cohorts of 3. After a cohort completed 4 weeks of treatment, a subsequent cohort could be initiated. Patients were required to complete 2 weeks at a given dose before the dose could be increased (by 25 mg *bid*). Dosing was initiated at 75 mg *bid* to 150 mg *bid*. Patients who responded, and then had their platelet counts decline, could have their dose further increased to a maximum of 175 mg *bid*. Eighteen patients entered the study and 2 patients remain on study.

In the twelve patients that responded to fostamatinib, the median platelet count increased from $16 \times 10^9/\text{L}$ at baseline to a median peak of $105 \times 10^9/\text{L}$. Twelve patients achieved at least 1 substantial platelet increase, which was sustained in 8 patients. Patients with a sustained response had increased platelet counts on at least 67% of occasions, and experienced a reduced need for IVIg treatment or a tapering of steroids while on the study drug. The median dose of fostamatinib for the 8 patients with sustained response was 125 mg *bid*. Four patients had a transient response to fostamatinib however these patients continued to take study drug due to an improvement in clinical parameters such as bleeding, need for rescue medications, and ability to taper steroids. There appeared to be no clinical differences between responders and non-responders.⁽¹⁾

Eighteen patients were included in the safety analysis during the initial treatment period. The 3 most commonly reported AEs were blood pressure increased (11 patients), petechiae

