5.3 Study Treatment

Depending on their response to treatment in Study C-935788-047 or C-935788-048 there will be two categories of subjects in this study: responders and nonresponders (see Figure 2).

- Responders will initiate open-label fostamatinib treatment with the dose and regimen that was efficacious in achieving a stable platelet response in Study C-935788-047 or C-935788-048.
- Nonresponders will initiate treatment with fostamatinib 100 mg PO *bid*. If a nonresponding subject has previously required a dose reduction (to less than 100 mg PO *bid*) due to an AE, the Sponsor's Medical Monitor should be contacted regarding the subject's eligibility and the appropriate starting dose.

Figure 2: Initial Treatment Allocation

Subjects will self-administer the study drug throughout the 60-month treatment period. Subjects on a *bid* dosing regimen will self-administer 1 tablet once in the morning and once in the evening at least 8 hours apart. Subjects on a *qd* dosing regimen will self-administer 1 tablet per day by mouth in the morning.

At the end of Month 1 (approximately Day 30), subjects receiving fostamatinib 100 mg PO *bid* should have the dose escalated to fostamatinib 150 mg PO *bid* if platelet count < 50,000/ μ L and the study drug is well tolerated (refer to [Section 7.2.1](#)).

Subjects whose platelet count is consistently < 50,000/ μ L following 3 months (12 weeks) of treatment, and at least 4 weeks at a dose of 150 mg PO *bid* (provided this higher dose was tolerated), should be discontinued from the study, unless tangible clinical benefit for the use of fostamatinib is evident and the Sponsor agrees (all instances must be reviewed with the Sponsor's Medical Monitor). Examples of tangible clinical benefit may include, but are not limited to:

- Credible increase in platelet count (eg, increase in platelet count of at least 20,000/ μ L over initial baseline to a count \geq 30,000/ μ L)
- Reduction in bleeding
- Reduction in the need for rescue therapy

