### **4.2 ITP History and Previous ITP Procedures**

ITP history, previous ITP procedures, and baseline characteristics include the followings:

- Baseline Platelet count(/uL)
- Baseline IBSL scores and baseline WHO Bleeding Scale scores
- Previous Splenectomy (Yes/No)
- Duration of ITP (years)
- Type of prior ITP (Persistent ITP or Chronic ITP)

- Prior ITP therapies
- Number of unique prior ITP therapies

Baseline Platelet count(/ $\mu$ L) is defined as last measurement prior to the first dose of fostamatinib, either the first dose of fostamatinib in Study C-935788-047 or C-935788-048 (for fostamatinib patients in the previous study) or the present study (for placebo patients in the previous study).

Baseline IBLs scores and baseline WHO Bleeding Scale scores, previous splenectomy (Yes/No), duration of ITP (years), type of prior ITP (Persistent ITP or Chronic ITP), prior ITP therapies and the number of unique prior ITP therapies are defined in the same way as presented for Study C-935788-047 or C-935788-048.

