### 4.3. Primary Efficacy Endpoint

**Version 1:** The first version of the primary efficacy endpoint is for the purpose of assessing efficacy among all patients while they are on active treatment in one of the prior studies, in the current extension study, or in both. This version of the primary efficacy endpoint is the achievement and maintenance of a stable platelet response defined as follows:

- 1) Achievement of a platelet count of at least 50,000/ $\mu$ L within 12 weeks of beginning active treatment and
- 2) Achievement of a sustained stable platelet response; defined as no two visits, at least 4 weeks apart, with a platelet count < 50,000/  $\mu$ L, without an intervening visit with a platelet count of  $\geq$  50,000/  $\mu$ L unrelated to rescue therapy, within a period of 12 months following initial achievement of the target platelet count (see above).

The beginning of active treatment may be in the prior study or in the present extension study, depending upon when the patient first received active treatment. Patients who discontinue treatment due to lack of efficacy or to an AE prior to 12 months following achievement of a platelet count of at least 50,000/ $\mu$ L will be considered failures.

**Version 2:** The second version of the primary efficacy endpoint is for the purpose of a within-patient, between-study comparison of fostamatinib and placebo among patients randomized to placebo in either of the prior studies, This version of the primary efficacy endpoint is the achievement and maintenance of a stable platelet response defined as follows:

- 1) Achievement of a platelet count of at least 50,000/ $\mu$ L within 12 weeks of beginning treatment (placebo treatment in the prior study and fostamatinib treatment in the present study) and
- 2) Achievement of a sustained stable platelet response; defined as no two visits, at least 4 weeks apart, with a platelet count < 50,000/  $\mu$ L, without an intervening visit with a platelet count of  $\geq$  50,000/  $\mu$ L unrelated to rescue therapy, within a period of 12 weeks following initial achievement of the target platelet count (see above).

Platelet counts taken within 28 days of rescue therapy will be excluded when determining the value of this endpoint. Patients who discontinue treatment or patients who are rescued prior to 12 weeks following achievement of a platelet count of at least 50,000/ $\mu$ L, will be considered failures.

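### Version 1 and duration of response ignore the pre-fostamatinib count, so prior-placebo patients already at 50,000/µL or more can be credited to the drug; a baseline-based sensitivity analysis is missing

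*SAP*

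**What the plan says.** **Version 1 (SAP 4.3).** Criterion 1 is "Achievement of a platelet count of at least 50,000"/µL within 12 weeks of starting active treatment. Criterion 2 is "Achievement of a sustained stable platelet response; defined as no two visits, at least 4 weeks apart, with a platelet count" under 50,000/µL (unless a qualifying higher count lies between them), judged over the following 12 months. Stopping treatment for lack of efficacy or an AE in that time is failure. SAP 10.1.1 reports one percentage with an exact interval.

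**Duration (SAP 4.4).** "Duration of platelet response will be defined as the length of time from when the patient first achieves a platelet count of at least 50,000"/µL, ending at the first of two visits under 50,000/µL. Protocol 10.4.2 ties this to the time after active treatment; SAP 4.4 leaves that qualifier out.

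**Additional durations (SAP 14.2).** Definitions 1 and 2 use "The length of time from when the patient first achieves a platelet count of at least 50,000"/µL; definitions 3 and 4 use "The length of time from when the patient first achieves a platelet count of at least 30,000"/µL. Loss is two consecutive visits below 30,000/µL (definitions 1 and 3) or below 20,000/µL (definitions 2 and 4), or first rescue.

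**Baseline.** SAP 4.2 says that the baseline platelet count "is defined as last measurement prior to the first dose of fostamatinib", which for prior-placebo patients falls in the present study. It serves the baseline tables and, through SAP 5.8, change from baseline. No visible response rule uses it.

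**Who can enter.** SAP 3.1 and Protocol 5.1 make patients at 50,000/µL or more at rollover a planned category. The allocation scheme in the Protocol synopsis includes placebo on the prior-study side. SAP 3.5 says that one such count was enough. SAP Table 3 has a row for placebo patients who were already stable responders.

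**The concern.** This is an uncontrolled extension, so apart from Version 2 the patient's own count before fostamatinib is the natural reference for a drug effect. A rule based only on an absolute count does not separate a patient raised to 50,000/µL by fostamatinib from one who was already there on placebo. Both add to the Version 1 percentage and to the Kaplan-Meier estimate of duration. The error runs one way: each such patient who keeps an unchanged count raises the reported result. As planned, the report would not show how many there are.

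**Working it through.** The plan has no sample size or expected response rate to reproduce, so the check applies the rules as written.

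**1. Unchanged count, no rescue, visits to Month 60.**
- Baseline 50,000/µL or more: Version 1 success. Duration runs from the Month 1 visit to Month 60, 60 − 1 = 59 months, censored, under SAP 4.4 and all four additional definitions.
- Baseline 45,000/µL: Version 1 failure and no response under SAP 4.4.

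The entire credit therefore depends on where the patient started.

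**2. Why Version 2 differs.** SAP 10.1.2 sets each patient's placebo-period status against the 049 status. A stable placebo responder falls in cell a or b and cannot count as a gain in cell c. Control is partial: a placebo patient with a single count of 50,000/µL at rollover, but no stable response, sits in the No row and can reach cell c. Version 1 and duration have no such pairing.

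**3. Size for Version 1.** Let N be treated patients, x Version 1 successes and k patients with baseline at 50,000/µL or more, all of whom succeed. Excluding them changes the percentage by

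x/N − (x − k)/(N − k) = k(N − x) / [N(N − k)],

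which is at most k/N because x ≥ k. The documents give none of these values. Assumed for illustration: N = 120, 45 prior-placebo patients, 5–15% of them at 50,000/µL or more.
- k: 45 × 0.05 = 2.25 and 45 × 0.15 = 6.75, so 2–7 patients.
- Upper bound: 2/120 = 1.7% and 7/120 = 5.8%, so 2–6 points.

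**4. Additional definitions.** Baselines at which the count rule cannot register a return to baseline:

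| Rule | Starts at (/µL) | Lost below (/µL) | Return to baseline not registered if baseline is |
|---|---|---|---|
| SAP 4.4 | 50,000 | 50,000 | 50,000 or more |
| Definition 1 | 50,000 | 30,000 | 30,000 or more |
| Definition 2 | 50,000 | 20,000 | 20,000 or more |
| Definition 3 | 30,000 | 30,000 | 30,000 or more |
| Definition 4 | 30,000 | 20,000 | 20,000 or more |

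Example: baseline 25,000/µL, one count of 30,000/µL at Month 1, then 25,000/µL throughout. Definition 3 records loss at Month 2, a duration of 2 − 1 = 1 month. Definition 4 records no loss from the counts. If the patient stops for lack of efficacy at Month 3, duration is 3 − 1 = 2 months (SAP 14.2 ends response there). If kept on treatment to Month 60 without rescue, it is 59 months, censored.

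**The case against.** Much of the case on the other side stands.

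- **Version 1 needs more than one count.** A reader might infer that a single count of 50,000/µL makes a Version 1 responder. It does not: 12 months of maintenance are required and stopping for lack of efficacy or an AE is failure. Protocol 3.1 also describes a low spontaneous remission rate, so the group may be small.
- **Response does end by other routes.** A reader might infer that a patient back at 20,000–30,000/µL can never lose response under definitions 2 and 4. Rescue ends it, and so does stopping for lack of efficacy or an AE. Protocol 5.3 and 7.3 say that patients who remain under 50,000/µL after 12 weeks, subject to a dose condition, should be discontinued unless benefit is evident and the sponsor agrees. What remains is the patient kept on under that exception.
- **The protocol's example of benefit is not an endpoint.** "Credible increase in platelet count (eg, increase in platelet count of at least 20,000"/µL over baseline, to at least 30,000/µL, might be read as a standard that SAP 14.2 contradicts. It is one of several non-exhaustive examples for continuing a nonresponder, so there is no contradiction.
- **The pilot data cannot size the problem.** Protocol 3.3 says "the median platelet count increased from" 16 × 10⁹/L, and one might fit a distribution to that. But the figure describes twelve responders in a population defined by counts below 30,000/µL, so it says nothing about the share above that level. The 047/048 entry criterion and baseline distribution are not in the documents.
- **Partial safeguards exist.** Main duration registers any return to a baseline below 50,000/µL. SAP 10.2.1 also reports duration for prior-fostamatinib Version 1 responders alone. SAP 14.2 is labelled additional and carries no test. None of this adjusts the Version 1 percentage or the overall duration for patients who began above the threshold.

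**Conclusion.** The point holds in a limited form. Version 1 and main duration can credit fostamatinib with counts that were present before the first dose, and neither analysis removes or displays them. The bias is upward whenever such patients keep their counts. Its size is unknown: 2–7 patients and at most 2–6 points rest on an assumed 45 of 120 and 5–15%, and the upper bound needs every one of them to sustain response. The sponsor holds the counts needed to replace these assumptions.

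The additional definitions are a secondary matter. Definitions 3 and 4 can start response with no rise. Definitions 2 and 4 can continue it after a return to a baseline of 20,000/µL or more, and definition 1 after a return to 30,000/µL or more, but only in patients kept on treatment without rescue. The exploratory endpoints in SAP 14.1 are redacted, so nothing is claimed about them. A missing sensitivity analysis is the finding; the main definitions need not be replaced.

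**What to change.** 1. **Version 1 and main duration.** Add a sensitivity analysis that excludes patients whose SAP 4.2 baseline count is 50,000/µL or more. Report the number excluded by prior treatment group. Show it beside the planned result, since some excluded patients may have benefited.
2. **SAP 14.2.** Repeat each definition in patients whose baseline is below its own loss threshold: below 30,000/µL for definitions 1 and 3, below 20,000/µL for definitions 2 and 4. Entry then always requires a rise, and a return to baseline falls below the loss threshold.
3. **Wording.** Restore in SAP 4.4 and 14.2 that the starting count is one taken after the first fostamatinib dose. State whether the 28-day rescue exclusion in SAP 5.1 applies to the baseline count used here.

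Do not add a loss rule of counts at or below the patient's own baseline: a patient with baseline 60,000/µL and two visits at 58,000/µL would lose response while above every threshold.

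The cost is a few lines of SAP text and one derivation from a baseline already defined. No new data are needed. The sensitivity figures may be slightly less favourable, and the restricted analyses will have fewer patients.
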